The mixing prior to administration strategy will involve withdrawal of 0.5 mL antigen from one vial of R21 Malaria vaccine and adding it to Matrix-M1 vial. 0.5 mL of R21 antigen shall be withdrawn from another vial of R21 Malaria vaccine and be added to the same Matrix-M1 vial. The total volume in Matrix-M1 vial will be 1.5 mL. After addition the content will be mixed gently, and 0.75 mL of the mixture will be withdrawn and administered to participants. Each dose of 0.75mL (after mixing of R21 with Matrix-M1) will contain 10 µg of R21 and 50 µg of Matrix-M1.

Administration of Vaccine: Vaccine preparation will be undertaken under aseptic conditions and in accordance with the trial SOPs. Vaccination administration and vaccine handling will be performed according to the relevant SOPs. The study participants will be observed closely for at least 30 minutes following the administration of study vaccine, with appropriate medical treatment readily available in case of an anaphylactic reaction.

2) Anti-malarial therapy

Participants in Arms 1 and 3 will receive three rounds of antimalarial drugs - each round starting on the day of vaccination (Day 0) at Study Months 0, 1, and 2. Each round consists of three daily doses of co-formulated dihydroartemisinin/piperazine on Day 0, 1, and 2 (i.e. the day of vaccination and each day for 2 days after). Dihydroartemisinin/piperazine tablets (Guilin Pharmaceutical Company or Sigma Tau Pharmaceuticals) for adult patients each contain 40 mg dihydroartemisinin and 320 mg piperazine with a therapeutic dose range between 2–10 mg/kg/day dihydroartemisinin and 16–26 mg/kg/dose piperazine (Table 3). In addition, each participant will receive a single low dose primaquine on the day of vaccination (Day 0) (Table 4). One single low dose primaquine of approximately 0.25 mg/kg (Thai Government Pharmaceutical Organisation) will be administered. This drug regimen has been used in mass drug administrations in more than 10,000 participants which have established that this antimalarial drug regimen is safe and clears gametocytes(15).

In the unexpected event that volunteers are found to be infected with malaria during screening, baseline or during follow-up examination they will be treated according to the most up-to-date government guidelines.

**Research Proposal Submission Form
for a study involving human subject enrollment WITH
specimen collection**

Document No.: FTM ECF-033-01

Page 18 of 52

Table 3. DHA-PIP dosing schedule

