Bodyweight in kilograms	One tablet contains 40mg DHA and 320 mg PIP		
	Number of tablets/day	Total tablets/month	Total tablets/study
≤ 50.0	2.5	7.5	22.5
> 50.0 to ≤ 60.0	3	9	27.0
> 60.0 to ≤ 70.0	3.5	10.5	31.5
> 70.0 to ≤ 85.0	4	12	36.0
> 85.0	5	15	45.0

Table 4. Primaquine dosing schedule

Bodyweight in kilograms	One tablet contains 15mg primaquine		
	Number of tablets/day	Total tablets/month	Total tablets/study
≤ 50.0	0.5	0.5	1.5
> 50.0 to ≤ 60.0	1.0	1.0	3.0
> 60.0 to ≤ 70.0	1.0	1.0	3.0
> 70.0 to ≤ 85.0	1.5	1.5	4.5
> 85.0	2.0	2.0	6.0

If the vomiting occurs within 30 minutes after the drug administration, the entire dose will be re-administered.

If the vomiting occurred between 30 and 60 minutes after the drug administration, the half dose will be re-administered.

In case the 2nd vomiting occur, the “administration of further study drug doses is left to the discretion of the treating physician if the patient wants to try again.

B6.2.1 Storage of vaccines and anti-malarial medications

The R21 vaccine antigen and Matrix-M adjuvant must be stored according to the manufacturer’s recommendations at +2°C to +8°C. Any temperature excursions outside the range +2°C to 8°C must be reported to the Jenner Institute and SIPL as soon as detected. Following an exposure to such a temperature deviation, vaccines will not be used until approval has been given by the study PI in consultation with Jenner Institute and SIPL. Study anti-malarial medications must be stored at room temperature below 30 degrees Celsius. All vaccines and study medications will be stored in a safe and locked place, with no access to unauthorized personnel. Only trained, authorized study staff will have access to the vaccines and study medications. Storage temperatures will be monitored daily, according to standard operating procedures (SOPs) at the investigator’s site. In addition, for vaccine storage refrigerator(s), an alarm system and a back-up refrigerator will be available in case of power failure/breakdown. All movements of the study vaccines will be documented and cold boxes, with temperature monitoring, will be used to transfer vaccines to the area where it will be administered.

**Research Proposal Submission Form
for a study involving human subject enrollment WITH
specimen collection**

Document No.: FTM ECF-033-01

Page 19 of 52

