APPENDIX D: HISTORY OF AMENDMENTS

Amendment No.	Protocol Version No.	Date issued	Author(s) of changes	Details of Changes made
1	4.0	24 August	[name]	
- Add new Co-investigator- Revise the severity grading of adverse event according to the recent PvDBPII/Matrix-M study
2	5.0	9 November	[name]	
- Change the Site Principal Investigator- Revise weight range for DHA-PIP dosing schedule (table 3) and Primaquine dosing schedule (table 4)- Add clarification of drug administration in case of vomiting- Include window period (+/- 1 day) for day 7 after vaccination (table 7)- Remove HLA typing

**Research Proposal Submission Form
for a study involving human subject enrollment WITH
specimen collection**

Document No.: FTM ECF-033-01

Page 52 of 52

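### The DHA-piperaquine dosing table gives less than the protocol's stated minimum dose to participants above 80 and up to 85 kg, and to those above 100 kg

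*Protocol*

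**What the plan says.** Protocol section B6.2, under anti-malarial therapy, says that the adult tablets "each contain 40 mg dihydroartemisinin and 320 mg piperazine", "with a therapeutic dose range between 2–10 mg/kg/day dihydroartemisinin and 16–26 mg/kg/dose piperazine (Table 3"). The word printed as piperazine is piperaquine, which Table 3 abbreviates to PIP. On frequency, the same section says: "Each round consists of three daily doses of co-formulated dihydroartemisinin/piperazine on Day 0, 1, and 2". There is one dose a day, so mg/kg per dose and mg/kg per day are the same quantity.

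Table 3 repeats the tablet strength ("One tablet contains 40mg DHA and 320 mg PIP") and sets five weight bands: 2.5 tablets a day up to 50 kg, 3 up to 60 kg, 3.5 up to 70 kg, then "> 70.0 to ≤ 85.0 4 12 36.0" and "> 85.0 5 15 45.0". In each row the figures after the weight band are tablets per day, per month and per study. Table 4 uses the same five bands for primaquine ("One tablet contains 15mg primaquine"), and the text gives the primaquine dose as approximately 0.25 mg/kg. Appendix D records that the weight ranges of both tables were changed in the same amendment: "Revise weight range for DHA-PIP dosing schedule (table 3) and Primaquine dosing schedule (table 4").

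**The concern.** The range and the table do not agree at two places on the weight scale. The first three bands each stop exactly where the dose falls to the stated minimum. The fourth runs 5 kg past that point, and the fifth has no upper end.

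The eligibility criteria in B5.2 set no maximum weight or body mass index. The only other dosing rule in B6.2 concerns re-dosing after vomiting. Staff who follow Table 3 exactly would therefore dose anyone in those two spans below the range the protocol states, at all nine daily doses (three rounds of three) if the weight stays in the span.

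What is at stake is limited. These are healthy, malaria-negative volunteers, so treatment failure is not the issue. Arms 1 and 3 use the same table, so the randomised comparison of piperaquine levels is not biased. But piperaquine level is a secondary endpoint, and the protocol should describe the dose given correctly.

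**Working it through.** **Inputs** (protocol B6.2 and Table 3): 40 mg DHA and 320 mg piperaquine per tablet; stated minimum 2 and 16 mg/kg; tablets per day by band as listed above.

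**Is the table read correctly?** Tablets per month should be 3 × the daily number and tablets per study 9 ×. All five rows agree, including 4/12/36 and 5/15/45, so the two upper rows are not a reading error.

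**Formulas.** DHA dose = 40 × tablets / kg. Piperaquine dose = 320 × tablets / kg. A band reaches the minimum at 320 × tablets / 16 = 20 × tablets kg. DHA gives the same weight (40 × tablets / 2), because 320/40 = 16/2 = 8. Both components therefore fall short at the same weights and by the same percentage.

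| Tablets/day | Band ends at | Minimum reached at | Piperaquine at band end (mg/kg) | DHA at band end (mg/kg) |
|---|---|---|---|---|
| 2.5 | 50 kg | 50 kg | 800/50 = 16.0 | 100/50 = 2.0 |
| 3 | 60 kg | 60 kg | 960/60 = 16.0 | 120/60 = 2.0 |
| 3.5 | 70 kg | 70 kg | 1120/70 = 16.0 | 140/70 = 2.0 |
| 4 | 85 kg | 80 kg | 1280/85 = 15.06 | 160/85 = 1.88 |
| 5 | no limit | 100 kg | none | none |

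**Size of the shortfall**
- 82.5 kg: 1280/82.5 = 15.52 mg/kg, 3.0% below 16.
- 85 kg: 15.06 mg/kg, 5.9% below.
- 105 kg: 1600/105 = 15.24 mg/kg, 4.8% below.
- 110 kg: 1600/110 = 14.55 mg/kg piperaquine and 200/110 = 1.82 mg/kg DHA, 9.1% below.

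**How many people.** The documents give no weight distribution, so this step is an assumption. Take normal weights truncated below at 38 kg, with mean 60, 65 or 70 kg and SD 10, 12 or 14 kg. The share above 80 and up to 85 kg is then 1.7% to 9.7%, or 1.2 to 6.8 of the 70 participants in Arms 1 and 3. The share above 100 kg is 0.0% to 1.6%, or 0 to 1.1 of 70. The mean shortfall among those affected is 2.5% to 3.1%.

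**Candidate repairs**
- Five tablets from just above 80 kg: at most 1600/80 = 20.0 mg/kg piperaquine and 200/80 = 2.5 mg/kg DHA, falling to 16.0 and 2.0 at 100 kg. All within range.
- 4.5 tablets for >80 to 90 kg: 1440/80 = 18.0 down to 1440/90 = 16.0 mg/kg piperaquine. Five tablets for >90 to 100 kg: 1600/90 = 17.8 down to 16.0.
- Primaquine in Table 4 (15 mg × tablets / kg): the present 1.5 tablets give 22.5/80 = 0.28 and 22.5/85 = 0.26 mg/kg. Moving the two-tablet row down to start above 80 kg would give up to 30/80 = 0.375 mg/kg.

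**The case against.** The arithmetic is not in dispute. The strongest objection concerns the reading. The sentence can be taken to describe the product's treatment range, with Table 3 as the operative instruction. Nothing says that every volunteer must receive at least 16 mg/kg, and a participant dosed by Table 3 can still meet the per-protocol requirement of complete, correct doses. This reading is possible, but two things weaken it: the sentence cites Table 3, and three of the five bands end exactly on the stated minimum. Even on this reading, the protocol calls a range therapeutic and then prescribes less without saying so.

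The second objection is size. Within the >50 to 60 kg band alone, piperaquine falls from 960/50 = 19.2 to 16.0 mg/kg, a drop of about 17%. A mean shortfall of 2.5% to 3.1% is small beside that. The number affected rests on assumed weights and could be about one, or none. This stands, and it is why no harm or bias is claimed.

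The third is proportion. Going from four to five tablets raises the daily dose by 25% to repair a gap of at most 5.9%, in healthy volunteers for whom Table 5 schedules one ECG. The higher dose stays within the stated range, but this is a fair reason to prefer 4.5 tablets or a change of wording.

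The fourth is that Table 4 departs further from its own target: 7.5/50 = 0.15 mg/kg at 50 kg, and 30/85 = 0.35 mg/kg just above 85 kg, against approximately 0.25. That is correct. It is a reason to review both tables together and does not answer the point about Table 3.

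**Conclusion.** The concern holds. Table 3 gives less than the stated minimum of both DHA and piperaquine to anyone above 80 and up to 85 kg, and to anyone above 100 kg. The shortfall reaches 5.9% at 85 kg, and above 100 kg it grows with weight (9.1% at 110 kg). These figures follow from the protocol alone. Only the headcount (about 1 to 7 of 70 in the first span, 0 to 1 in the second) depends on assumed weights.

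It is a modest internal inconsistency in a dosing rule. It should be corrected, but it threatens neither participant safety nor the comparison of Arm 1 with Arm 3.

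**What to change.** The clinical choice is the sponsor's.

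**Option A: change the table.** End the four-tablet band at 80 kg. Then give either 5 tablets for >80 to 100 kg, or 4.5 tablets for >80 to 90 kg and 5 for >90 to 100 kg. Add a rule above 100 kg. Do not carry the new cut-off into Table 4 automatically: its 1.5 primaquine tablets can stay up to 85 kg. Cost: a dosing-table amendment and a check of Table 4.

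**Option B: change the wording.** Keep Table 3, state the range it actually delivers (down to 15.06 mg/kg piperaquine and 1.88 mg/kg DHA at 85 kg), and add a rule above 100 kg. Cost: a sentence or two.

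Neither option changes the sample size or the analysis.

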- 11) Positive malaria parasitaemia (RDT) at screening or baseline (Month 0, Day 0).
- 12) Receipt or planned receipt of an investigational medical product or participation in an interventional clinical trial during the study period
- 13) Contraindications to the use of artemisinins, piperaquine or primaquine*.
- 14) Use of medications with known potential interactions, prior allergic reactions to one or more components of the drug regimen.
- 15) History of allergic disease or reactions likely to be exacerbated by any component of the vaccine (e.g. egg products)
- 16) History of clinically significant contact dermatitis.
- 17) Contraindication to intramuscular (IM) injection*

**Research Proposal Submission Form
for a study involving human subject enrollment WITH
specimen collection**

Document No.: FTM ECF-033-01

Page 11 of 52

- 18) Administration of a vaccine not included in the study protocol within 7 days of a study vaccine^c.
- 19) History of anaphylaxis post-vaccination.
- 20) Administration of immunoglobulins and/or any blood products during the period starting three months before the first dose of study vaccine or planned administration during the study period.

* subject to the investigator's judgement

Exceptions:

^a Inhaled and topical steroids.

^b Participation in hepatitis C vaccine study with confirmed negative HCV antibodies prior to participation in that study, and negative HCV RNA PCR at screening for this study

^c The following vaccinations may be administered more than 7 days before or after a study vaccination: polio, diphtheria, tetanus, pertussis, hepatitis B, Haemophilus influenzae type b, Bacillus Calmette–Guérin (BCG vaccine), measles, influenza, pneumococcal disease, COVID-19 or yellow fever

B5.3 Sample size calculation

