Informed Consent		x																		
Eligibility screen		x																		
Inclusion / Exclusion criteria		x	x				x				x									
Enrolment			x																	
Allocation			x																	
Interventions	Vaccination (Group 1 and Group 2)		x				x				x									
	DHA/piperazine (Group 1 and Group 3)		x	x	x		x	x	x		x	x	x							
	PQ (single low dose primaquine) (Group 1 and Group 3)		x				x				x									
Assessments	History of fever, current axillary temperature*	x	x	x	x	x	x	x	x	x	x	x	x	x	x	x				
	Full medical history, vital signs, physical examination	x	x				x				x									
	Ask about any concomitant medication	x	x	x	x	x	x	x	x	x	x	x	x	x	x	x				
	Assessment of any adverse event(s)		x	x	x	x	x	x	x	x	x	x	x	x	x	x				
	Assess for any withdrawal criteria		x	x	x	x	x	x	x	x	x	x	x	x	x	x				
	Blood tests						Unit (mL)													
	P. falciparum test**						0.5				0.5					0.5				
	CBC	2	2			2				2				2						
	Biochemistry ALT, AST, CREA, BUN, Bilirubin	3	3			3				3				3	3					
	HBsAg, HCV, HIV	1																		
	Immunology panel ^b		20				20				20				20	20				
	Piperazine levels***		1	1	1	1	1	1	1	1	1	1	1	1						
	Blood volume per visit (mL)	6	26	1	1	6	21.5	1	1	6	21.5	1	1	6	25	20.5				
	Maximum cumulative blood volume (mL)															144.5				
Electrocardiogram (ECG)		x																		

**Research Proposal Submission Form
for a study involving human subject enrollment WITH
specimen collection**

Document No.: FTM ECF-033-01

Page 21 of 52

Urine pregnancy test	x	x				x				x					
Diary card provided		x				x				x					
Diary card return						x				x					x

* Axillary temperature will be recorded from D0-D7 visits after each vaccination. If the symptoms are indicated to COVID-19, COVID-19 test will be done. If COVID-19 positive is indicated, then hospital guideline for COVID-19 case management will be followed. Study team will make decision whether or not to withdraw volunteer from the study case by case.

** *P. falciparum* test for purposes of indicating whether volunteer has been exposed, and not as an assessment of protection.

*** Piperaquine levels for group 1 and 3 only. Additional drug level assessment for Primaquine will be done, if additional data are required. Blood sample will be collected before each dose (at each visit) and then at day 7 for drug levels assessment.

- a. first day of M6
- b. the immunology panel consists of assays to be processed at UK laboratories and may include:

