DHA-PIP is the first line treatment for uncomplicated malaria in many malaria endemic countries in Asia and Africa and has an extraordinary robust safety profile (16-18). DHA-PIP is also very well tolerated. The main reported side effects are gastrointestinal upset (nausea, vomiting, abdominal pain and diarrhoea) as well as dizziness, headache and disturbed sleep. Rates of these side effects

Research Proposal Submission Form for a study involving human subject enrollment WITH specimen collection

Document No.: FTM ECF-033-01

Page 32 of 52

are generally < 10% and often <5% except for dizziness (~12%). There is no evidence that DHA-PIP can cause clinically significant QTc prolongation at therapeutic doses(19).

Primaquine (PQ)

Like all 8-aminoquinolones, primaquine is associated with haemolysis in G6PD deficient individuals in a dose-related relationship. To avoid any potential risk for haemolysis, participants will receive just a single low dose of primaquine (approximately 0.25mg/kg) on the day of vaccination, at each vaccine dose (for groups 1) and on Day 0 at each round of antimalarial drugs for three rounds (for group 3). This dose is safe even when administered to individuals with a genotype associated with severe G6PD deficiency(20). Other known side effects with primaquine administration include symptoms of gastritis and enteric complaints when administered for 14 days at large doses for the treatment of *Plasmodium vivax* malaria. Such abdominal complaints have not been observed when a single low dose primaquine is administered.

C2.2 Preventive and alleviative measures for risk

Phlebotomy

Participants' blood samples will be collected by well-trained medical personnel with aseptic technique to prevent infection or complications.

R21/Matrix-M™ vaccination

Volunteers will be vaccinated in a clinical area where Advanced Life Support trained physicians, equipment and drugs are immediately available for the management of any immediate post-vaccination serious adverse reactions. Participants will be observed closely for at least 30 minutes following administration of the vaccine. No SAEs attributable to the R21/Matrix-M™ were detected during the large trial in Burkina Faso.

Antimalarial medications

Dihydroartemisinin/piperaquine (DHA-PIP)

To exclude the possibility that pre-existing QTc prolongation results in AEs, the QTc of all volunteers will be measured and candidates with a QTc>450ms will not be enrolled.

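### The primaquine dose stated as about 0.25 mg/kg, on which the haemolysis statement rests, is not reconciled with Table 4 (0.150 to 0.353 mg/kg at band edges); Table 3 also falls below its stated range at some weights

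*Protocol*

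**What the plan says.** Arms 1 and 3 (50 + 20 = 70 participants) are to take primaquine on Day 0 of three monthly rounds. Protocol B6.2, item 2 (Anti-malarial therapy), points to Table 4 for the schedule and in the next sentence gives the dose: "One single low dose primaquine of approximately 0.25 mg/kg". No range or tolerance is attached. Table 4 is written in tablets ("One tablet contains 15mg primaquine") across five weight bands, the last with no upper limit.

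C2.1 builds its risk statement on the same figure. It says that "primaquine is associated with haemolysis in G6PD deficient individuals in a dose-related relationship". It then says: "To avoid any potential risk for haemolysis, participants will receive just a single low dose of primaquine (approximately 0.25mg/kg) on the day of vaccination". It concludes: "This dose is safe even when administered to individuals with a genotype associated with severe G6PD deficiency".

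For the partner drug, B6.2 does state a range: 2–10 mg/kg/day dihydroartemisinin (DHA) and 16–26 mg/kg/dose piperaquine, with a pointer to Table 3 (tablets of 40 mg DHA and 320 mg piperaquine).

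The SAP does not give doses by weight.

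**The concern.** The text gives mg/kg and the table gives tablets, so a reader has to divide to see what each participant would receive. The division gives a spread around 0.25 mg/kg that no section states, and at some weights the excess is large.

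This matters because C2.1 rests a safety statement on that number. It makes the size of the dose the protection against a dose-related harm. Within the risk section nothing else is written against haemolysis. C2.2 has a measure for the partner drug ("To exclude the possibility that pre-existing QTc prolongation results in AEs, the QTc of all volunteers will be measured") but no entry for primaquine. The safety bloods in Table 5 are a blood count and "Biochemistry ALT, AST, CREA, BUN, Bilirubin"; no G6PD test is listed. An ethics committee reading C2.1 would take the statement to describe the dose given in every weight band, and the documents do not show that it does.

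The Table 3 point is separate and smaller: a stated dose range is not met at some weights by the table cited for it.

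**Working it through.** **Inputs.** Stated primaquine dose 0.25 mg/kg (B6.2, C2.1). Tablet 15 mg; tablets per dose 0.5, 1, 1, 1.5 and 2 by band (Table 4). Stated minimums of 16 mg/kg piperaquine and 2 mg/kg DHA (B6.2). Tablet 320 mg piperaquine and 40 mg DHA; tablets per day 2.5, 3, 3.5, 4 and 5 by band (Table 3).

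**Step 1: where Table 4 reproduces the stated figure.** Weight = mg / 0.25. This gives 7.5/0.25 = 30 kg, 15/0.25 = 60 kg, 22.5/0.25 = 90 kg and 30/0.25 = 120 kg. The 90 kg value lies outside its own band (>70 to 85 kg), so Table 4 gives exactly 0.25 mg/kg only at 30, 60 and 120 kg.

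**Step 2: band edges.** mg/kg = tablets × 15 / weight. Lower-edge values are the limits just above the edge.

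| Band (kg) | Dose (mg) | Just above lower edge | At upper edge |
|---|---|---|---|
| ≤50 | 7.5 | – | 7.5/50 = 0.150 (−40%) |
| >50 to 60 | 15 | 15/50 = 0.300 (+20%) | 15/60 = 0.250 (0%) |
| >60 to 70 | 15 | 15/60 = 0.250 (0%) | 15/70 = 0.214 (−14%) |
| >70 to 85 | 22.5 | 22.5/70 = 0.321 (+29%) | 22.5/85 = 0.265 (+6%) |
| >85 | 30 | 30/85 = 0.353 (+41%) | none; 30/100 = 0.300, 30/120 = 0.250 |

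The dose exceeds 0.25 mg/kg at >50 to <60 kg and at every weight above 70 and below 120 kg.

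**Step 3: how much depends on the word approximately.** No tolerance is given, so four are assumed. Weights above each limit:

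- +10% (0.275): >50 to <54.5, >70 to <81.8 and >85 to <109.1 kg
- +20% (0.300): >70 to <75 and >85 to <100 kg
- +30% (0.325): >85 to <92.3 kg
- +40% (0.350): >85 to <85.7 kg

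**Step 4: how much tablet size can explain.** Half-tablet steps are 7.5 mg. This tests the stated figure and proposes no schedule.

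- Just above 50 kg: 0.25 × 50 = 12.5 mg. The adjacent steps are 7.5 mg (−40%) and 15 mg (+20%). Table 4 gives 15 mg, the nearer.
- Just above 70 kg: 0.25 × 70 = 17.5 mg. The adjacent steps are 15 mg (−14%) and 22.5 mg (+29%). Table 4 gives 22.5 mg, one step up. It becomes the nearer step at 18.75/0.25 = 75 kg.
- Just above 85 kg: 0.25 × 85 = 21.25 mg. The adjacent steps are 15 mg (−29%) and 22.5 mg (+6%). Table 4 gives 30 mg, beyond both. It becomes an adjacent step only at 22.5/0.25 = 90 kg, and the nearer one at 26.25/0.25 = 105 kg.

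Tablet size therefore accounts for the excess at >50 to 60 kg. It also accounts for the excess above 70 kg if one step of rounding up is accepted. It does not account for the excess just above 85 kg.

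**Step 5: Table 3 against its stated range.** mg/kg at the upper edge of each band:

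| Upper edge (kg) | Piperaquine | DHA |
|---|---|---|
| 50 | 800/50 = 16.0 | 100/50 = 2.0 |
| 60 | 960/60 = 16.0 | 120/60 = 2.0 |
| 70 | 1120/70 = 16.0 | 140/70 = 2.0 |
| 85 | 1280/85 = 15.06 | 160/85 = 1.88 |

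The first three bands end exactly on both minimums. The fourth reaches them at 1280/16 = 160/2 = 80 kg, so it is below them at >80 to 85 kg, by 1 − 15.06/16 = about 6% at 85 kg. The open top band reaches them at 1600/16 = 200/2 = 100 kg and is below them at any higher weight.

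**The case against.** The protocol says approximately, and five bands with 15 mg tablets must spread around any nominal dose. B6.2 cites Table 4 next to the nominal figure, so the two are presented together. Appendix D records that the weight ranges of Tables 3 and 4 were revised in version 5.0, so the bands look deliberate. The safety sentence in C2.1 cites a published study, and whether its support stops at 0.25 mg/kg or extends to 0.35 cannot be judged from these documents. B6.2 also cites use of the regimen in more than 10,000 participants.

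Much of this stands. It rules out calling the text and table contradictory at every weight, and it rules out saying that tablet size explains none of the high side. It does not make +41% consistent with an unqualified 0.25 mg/kg, and it does not explain values below a minimum that the protocol itself states.

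A reader might infer that heavier participants would receive an unsafe dose, or that nothing guards against haemolysis. The documents support neither. Exclusion 13 covers "Contraindications to the use of artemisinins, piperaquine or primaquine", subject to the investigator's judgement. Haemoglobin below 10 g/dL is an exclusion. Haemoglobin and bilirubin are measured on Day 7 of every round and at Month 3, and anaemia at later rounds is treated under national guidelines (B6.4.6). The absence of other measures is a feature of the risk section, not of the whole plan.

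**Conclusion.** The concern holds as a failure to reconcile text and tables. For primaquine, a dose stated without tolerance, and relied on in the haemolysis statement, corresponds to 0.150 mg/kg at 50 kg, up to 0.321 just above 70 kg and up to 0.353 just above 85 kg. Only the doses above 0.25 mg/kg bear on the haemolysis statement; the low value at 50 kg is a mismatch with the stated dose only. The high-side mismatch is clearest just above 85 kg, where neither half-tablet rounding nor a tolerance of up to 40% removes it. For DHA-piperaquine, Table 3 is below both stated minimums at >80 to 85 kg and above 100 kg.

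The mg/kg figures rest only on the printed tablet strengths and bands. How many weights count as outside approximately depends on the assumed tolerance in step 3. The number of participants affected is unknown, because no weight distribution or limit is given; at most the 70 in Arms 1 and 3 take these drugs. It would also go too far to infer a dispensing error or a biased comparison of piperaquine levels: the documents give no sign of the first, and Arms 1 and 3 follow the same tables.

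**What to change.** The investigators should reconcile the dose statements in B6.2 and C2.1 with Tables 3 and 4. They should also state, by weight band, the delivered primaquine mg/kg range that the C2.1 haemolysis statement is meant to cover. Whether the text or the tables change is for them to decide; this review takes no position on which dose is right.

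The cost is a correction of wording or tables in the protocol, submitted for approval like any other amendment (Appendix B, 2.5). It needs no new procedure and no new data. If a table changes, its monthly and study tablet totals must change with it.
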